29 a "morselized, flowable tissue allograft derived from amniotic tissues. Amniotic tissues have been shown
30 to support soft tissue repair, reduce inflammation and minimize scar tissue formation".^{6,7}

31

32 This study will compare corticosteroid injection to BioDRestore injection in patients with significant
33 (Kellgren-Lawrence grade 3-4) knee osteoarthritis. Our hypothesis is that BioDRestore will result in
34 better outcomes than corticosteroid when injected intra-articularly in patients with knee OA.

35

36 **2. Study Endpoints**

37

38 Primary Endpoint

- 39 • Visual Analog Score (VAS), VR-12, Lysholm, SANE and Knee Injury and Osteoarthritis
40 Outcome Score (KOOS) at the 6-week, 3-month, 6-month, and 12-month post-injection time
41 periods.

42

43 Secondary Endpoints

- 44 • Inflammatory markers at 6-months post-injection.

45

46 **3. Subject Recruitment and Screening**

47

48 *Screening*

49 Patients who present with osteoarthritis of the knee and are recommended for a knee
50 injection will be screened for inclusion into the study. Following discussion of the
51 study between the patient and the treating physician, the patient will be given the
52 opportunity to move forward with the informed consent process.

53

54 *Enrollment*

55 The subject will be considered enrolled once voluntary informed consent has been
56 given, and the form has been signed and dated by all required parties.

57

58 *Randomization*

59 Subjects will be randomized to a treatment arm (corticosteroid or BioDRestore injection)
60 using a 1:1 ratio. Once study eligibility has been confirmed, the study coordinator or
61 designee will randomize the subject to a treatment arm. The treatment for each subject
62 will be assigned through the study database.

63
64
65
66
67
68
69
70
71
72
73
74
75
76
77
78
79
80
81
82
83
84
85
86
87
88
89
90
91
92
93
94
95
96
97
98
99
100
101
102
103
104
105
106
107
108
109
110
111
112

Blinding

Study subjects and investigators will be blinded to the treatment assignment for the duration of the study to reduce the risk of bias. The research coordinator will provide the randomization to the investigator’s medical assistant (MA) prior to treatment in order for the MA to assist with preparation of the injection.

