- Patient Outcomes: Subject to complete VAS, VR-12, KOOS, Lysholm and SANE prior to injection.
- Range of Motion Assessment: Measurement taken using goniometer.

Visit 2- Randomization & Procedure

- **Inclusion/Exclusion review**
- **Randomization**
- Procedure: For patients with current knee effusion, the investigator will drain the effusion prior to the injection. For subjects that do not exhibit any signs of knee effusion, the investigator will proceed with the injection. Study subjects will be randomized to receive a cortisone or BioDRestore injection. Subjects will be blinded to the assignment. Prior to the injection, the area will be prepared with sterile solution and numbing agent. Next, an injection of one of the following treatments, dependent on randomization, will be injected into the articular space of the knee:

_2 cc of 40 mg/ml Kenalog with 3 cc of saline

_2 cc BioDRestore with 3 cc of saline

Knee arthrocentesis (for procedure, see below under "Follow-up Visits"): The study doctor will attempt to perform a knee aspiration to provide a delta value for the assay.

Follow-Up Visits (6WK, 3M, 6M, 12M)

The following information will be collected at each follow-up visit:

- 162 • Patient Outcomes: Subject to complete VAS, VR-12, KOOS, Lysholm, and SANE scales
163 • **6-month only, subject will return to the clinic for the following:**
164 ▪ Range of motion assessment
165 ▪ Knee arthrocentesis (aspiration): The area will first be prepared with sterile
166 solution and numbing agent. Using a 10-mL syringe, obtain at least
167 0.25mL of synovial fluid via a parapatellar approach. A knee aspiration
168 attempt will be made on all subjects that produced an adequate sample at
169 baseline prior to the injection. Upon completion, the syringe will be
170 labeled and transported to the Clemson Bioengineering Laboratory of
171 Orthopaedic Tissue Regeneration & Orthobiologics lab for analysis.
172 ▪ Aspirate analysis: Enzyme linked immunosorbent assay (ELISA) will be
173 performed on synovial fluid aspirated from the knees of study patients at 6
174 months post-injection to determine if there are quantitative differences in
175 soluble mediators and products of osteoarthritis. Briefly, synovial fluid
176 samples will be evaluated in duplicate for inflammatory (interleukin-1 beta;
177 IL-1 β and tumor necrosis factor-alpha; TNF- α), anti-inflammatory
178 (interleukin-1 receptor agonist; IL-1RA and interleukin-10; IL-10), pain

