179 (prostaglandin-E₂; PGE₂) and soluble signals which indicate cartilage
180 damage (S100A8 and S100A9 proteins, respectively).
181
182 Briefly, frozen (-80°C) samples will be thawed and analyzed using a
183 bicinchoninic acid assay (BCA) to normalize for total protein content.
184 Samples will be diluted accordingly using calibrator diluent supplied with
185 ELISA kits. ELISA will be performed according to manufacturer's protocols
186 and well plates will be analyzed optically on a μ -Quant microplate reader.
187 Concentrations will be determined using a standard curve developed from
188 known concentrations of supplied analyte. Experimental sample analyte
189 concentrations (ng/ml) will be plotted on histograms and group mean
190 concentrations \pm standard deviation will be calculated for each experimental
191 group.
192 • **12-month only, subject will return to the clinic for the following:**
193 ○ Range of motion assessment
194 ○ Radiographs of affected knee
195 • **Allowed Concomitant Medications and Prohibited Treatments**
196 ○ Concomitant Medications: Patients are allowed acetaminophen and/or ibuprofen
197 for the first 6 months following treatment.
198 ○ Prohibited Treatments: Oral steroids, steroid injections and Viscosupplementation
199 are not permitted for the first 6 months of the study in the treated knee.
200

201 6. Risk Analysis

202 *Potential Risks*

203 Mild pain and discomfort at the injection site are normal and expected reactions. While
204 rare, complications may occur due to either the cortisone injection or study injection.

205 These include the following:

- 206 • Infection
- 207 • Post-injection flare
- 208 • Localized subcutaneous or cutaneous atrophy
- 209 • Skin discoloration
- 210 • Stiffness

211
212
213
214
215
216
217
218
219
220
221
222
223
224
225
226
227
228
229
230
231
232
233
234
235
236
237
238
239
240
241
242
243
244
245
246
247
248
249
250
251
252
253
254
255
256
257
258

Potential Benefits

Participation in this study may offer no benefit to subjects. However, it is possible that the use of BioDRestore will result in better outcomes than corticosteroid when injected intra-articularly in patients with knee OA.

Study subjects will receive a \$50 stipend for each study visit for a total of \$300 if all visits are completed.

7. Adverse Events

Definitions

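### The 6-month marker means cover only knees that still yield fluid after treatment, so randomization does not protect their comparison; the direction of any bias is unknown, and no analysis of failed taps is planned

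*Combined protocol and SAP*

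**What the plan says.** Section 2 gives the secondary endpoint as "Inflammatory markers at 6-months post-injection". Section 5 (Follow-Up Visits, 6-month items) states that the assay is "performed on synovial fluid aspirated from the knees of study patients at 6" months; no other source of material is named.

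Two conditions decide who contributes:

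- **Before the injection.** A 6-month aspiration "attempt will be made on all subjects that produced an adequate sample at" baseline. The baseline tap takes place at Visit 2, where the study doctor will "attempt to perform a knee aspiration to provide a delta value for the assay".
- **After treatment.** The 6-month tap is to collect at least "0.25mL of synovial fluid via a parapatellar approach".

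For analysis, Section 5 says that group mean "concentrations \pm standard deviation will be calculated for each experimental" group. Section 11.2 names no test for the markers. Section 11.1 states intention to treat and chained-equations multiple imputation, next to the drop-out allowance, without mentioning markers or unsuccessful aspirations. The plan contains no rule for analysing a dry or inadequate tap, no comparison of fluid yield by arm and no expected number of samples.

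Visit 2 also states: "For subjects that do not exhibit any signs of knee effusion, the investigator will proceed with the injection". How this fits with the attempted baseline aspiration is not explained.

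**The concern.** Whether a knee yields fluid at 6 months is itself an outcome. Either injection could change it, and so could natural fluctuation or the difficulty of the tap. If yield is related to marker level and differs by arm, the knees left in one arm are not comparable with those left in the other, even though allocation was random. The difference in means then mixes the treatment effect on the markers with a difference in who could be sampled.

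The baseline condition is of another kind. It is settled before the injection, so treatment cannot affect it; it limits the number of samples and the population described.

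Analysing change from baseline would not help, because a change also needs a 6-month sample. What is at stake is how far the sole secondary endpoint can be read as a treatment effect. The proportion of knees that no longer yield fluid may also be informative, and it is not analysed.

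**Working it through.** **The plan's own figure.** There is none for the markers. The stated minimum of 70 is for the five patient-reported outcomes. A MANOVA global-effects calculation (Pillai trace, f² = 0.20, 2 groups, 5 responses, alpha 0.05) gives N = 70 with power 0.801, so it reproduces, but it does not bear on this point.

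**Inputs from the documents.** About 35 per arm (Section 11.1), the fluid target and the mean ± SD summary (Section 5).

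**Assumed inputs, not in the documents.** Marker SD 1. A latent fluid volume with correlation ρ to the marker. Comparator yield 80% or 50%. True difference δ (BioDRestore lower by 0.5 SD, or zero). A shift e in dryness not acting through the marker: e = +0.5 makes BioDRestore knees drier, e = −0.5 makes comparator knees drier.

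**Formula.** Let a_C be the normal cut-off for comparator yield, a_T = a_C + ρδ + e, and λ(a) = φ(a)/[1 − Φ(a)]. Then

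observed difference = −δ + ρ[λ(a_T) − λ(a_C)].

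Worked case: ρ = 0.5, comparator yield 80%, e = 0.5, δ = 0.5. Here a_C = −0.842 and λ(a_C) = 0.350; a_T = −0.842 + 0.25 + 0.5 = −0.092 and λ(a_T) = 0.740. The observed difference is −0.5 + 0.5 × (0.740 − 0.350) = −0.305, with a BioDRestore yield of 53.7%.

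| True difference | ρ | Dryness shift e | Observed, comparator yield 80% | Observed, comparator yield 50% |
|---|---|---|---|---|
| −0.50 | 0.5 | 0 | −0.443 | −0.417 |
| −0.50 | 0.5 | +0.5 | −0.305 | −0.235 |
| −0.50 | 0 | +0.5 | −0.500 | −0.500 |
| −0.50 | 0.5 | −0.5 | −0.548 | −0.576 |
| −0.50 | −0.5 | +0.5 | −0.557 | −0.583 |
| 0 | 0.5 | +0.5 | +0.122 | +0.172 |
| 0 | 0.5 | −0.5 | −0.086 | −0.144 |

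So the bias can be absent, towards the null, away from it, or a difference where none exists.

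**A narrower model.** If the chance of a usable tap depends on the marker alone, as logistic(0.5 + b × marker), simulation turns a true 0.50 SD into 0.47, 0.42 or 0.32 SD for b = 0.5, 1 or 2, with usable taps in about 62/56%, 60/50% and 58/42% of the arms. A true 0.80 SD becomes 0.76, 0.67 or 0.50 SD. This model cannot settle direction: it also shrinks the difference with the slope reversed (b = −1 gives about 0.43 for 0.50), because it leaves no other route from treatment to fluid volume.

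**Precision.** Power for 0.5 SD is Φ(0.5√(n/2) − 1.96). With n = 35 per arm it is 55%. If half the knees pass at baseline and half at 6 months, n = 35 × 0.5 × 0.5 = 8.75 and power is 18%.

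**The case against.** **A reader might infer that the bias runs towards no difference**, because a treatment that settles inflammation would dry out its own responders. The documents do not support this as fact. They do not say that either injection resolves effusion, that yield follows marker level, or which arm would have more dry knees. The comparator is an active steroid that could also reduce fluid. The panel includes IL-1RA and IL-10, listed as anti-inflammatory, so one direction need not fit every marker. Attenuation is one possibility among several.

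**A reader might infer that small samples and dry-tap results are thrown away.** The volume is a collection instruction; nothing says that less is discarded, and Section 9 requires source records for each assessment. What is missing is an analysis of those results.

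**Multiple imputation may be meant to cover the markers.** Its scope is unclear. Even if it does, imputation under missing at random would not remove the bias if dryness depends on the unseen marker level.

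**The Visit 2 sentences need not contradict each other.** Going ahead with the injection may mean only that there is no effusion to drain, and the Schedule of Events lists aspiration at the treatment visit. The wording is unclear rather than plainly inconsistent.

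**The effect may be small beside the noise.** This is fair. In the worked case, with 35 attempted per arm, 28 and about 18.8 samples remain; the standard error is √(1/28 + 1/18.8) ≈ 0.30 SD against a bias of about 0.20 SD. That limits the severity. It does not turn the subset into a randomized comparison.

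**Conclusion.** The point holds as selection on a post-randomization outcome with no planned handling, in a secondary endpoint that was not separately powered. The comparison of marker means is not protected by randomization, and the direction of bias is unknown. It is towards no difference if the more effective arm loses more low-inflammation knees; it can also go away from the null or create a difference; and it is absent if yield is unrelated to marker level.

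For correlations of ±0.5 and the yields shown, the bias is at most about 0.27 SD (0.50 observed as 0.235). These sizes rest wholly on assumed correlations, yields and dryness shifts, so they show what is possible, not what is expected. The point calls for a cheap improvement; it does not invalidate the trial.

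**What to change.** 1. For every knee in which a 6-month tap is attempted, record the volume and whether the tap was adequate, dry or a technical failure.
2. Compare the proportion with an adequate tap between arms, among all attempted knees, as part of the secondary endpoint. Because the baseline condition precedes the injection, this comparison keeps the protection of randomization, apart from drop-out and missed visits. Report it with a confidence interval: at 35 per arm, yields of 80% and 53.7% differ by 26 points with a 95% half-width of 1.96 × √[(0.80 × 0.20 + 0.537 × 0.463)/35] ≈ 21 points.
3. Describe the marker means as applying to knees with aspirable fluid at baseline and at 6 months.
4. Add a sensitivity analysis over all attempted knees that places dry taps by a pre-stated, marker-specific rule, with both favourable and unfavourable bounds and technical failures kept separate. Ranking every failed tap as most favourable would be hard to defend for IL-1RA and IL-10, and would count technical failures as success.
5. State whether the multiple imputation in Section 11.1 covers the markers.
6. Clarify how the two Visit 2 sentences apply to knees without effusion.

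The cost is one form field, a little more analysis and a more cautious marker conclusion. No procedure is added.

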An adverse event is defined as any untoward medical occurrence in a clinical investigation in which a subject is administered a study device and which does not necessarily have a causal relationship with the device. An adverse event can therefore be any unfavorable and unintended sign (including an abnormal laboratory finding or an abnormal radiographic finding), symptom, or disease temporally associated with the use of study device, whether or not related to the study device. The following are specific definitions of adverse events:

Adverse Event (AE) — any untoward medical occurrence in a subject, regardless if there is a relationship between the AE and the device.

Adverse Reaction (AR)- The FDA requires, per 21CFR 1271.350(a), the reporting of certain adverse reactions related to implantation, transplantation, infusion or transfer of an HCT/P. For tissue products, an Adverse Reaction is any unintended response, including a communicable disease, in the recipient of a human tissue or cell product implantation or transplantation. An Adverse Reaction is considered serious (SAR) if it meets the criteria of a Serious Adverse Event (see below).

Serious Adverse Event (SAE) — an adverse event that:

- leads to a death
- leads to a serious deterioration in the health of a subject that results in a life-threatening illness or injury
- results in a permanent impairment of a body structure or a body function
- requires in-subject hospitalization or prolongation of existing hospitalization
- results in medical or surgical intervention to prevent permanent impairment to body structure or a body function
- results in congenital anomaly/birth defect

Treatment for Adverse Events

In the event of an adverse event, the investigator and/or other professional personnel in attendance will provide whatever appropriate medical treatment is indicated for the problem.

Documentation of Adverse Events

All adverse events will be documented in the source documentation. Beginning after the study procedure has taken place, all AE's, including those measured, observed or volunteered, will be recorded on the applicable case report form. The investigator will review all documentation (e.g., hospital progress notes, laboratory, or diagnostic reports)

259 relative to the event being reported. The investigator will then record all relevant
260 information regarding an AE onto the study CRF.

261
262 The investigator will attempt to establish a diagnosis of the event based on signs,

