263 symptoms, and/or other clinical information. In such cases, the diagnosis should be
264 documented as the AE and not the individual signs and symptoms.

265 When reporting an AE, the investigator will evaluate the event for duration, intensity,
266 relationship and outcome.

267
268 Examples of an AE:

- 269 ▪ Exacerbation of a chronic or intermittent pre-existing condition including either
270 an increase in frequency or intensity of the condition.
- 271 ▪ Significant or unexpected worsening or exacerbation of the condition/indication
272 under study.
- 273 ▪ A new condition detected or diagnosed after study device administration even
274 though it may have been present prior to the start of the study.
- 275 ▪ Pre- or post-procedure events that occur as a result of protocol-mandated
276 procedures (e.g., invasive protocol-defined procedures, modification of a
277 subject's previous treatment regimen).

278
279 An AE Does NOT Include:

- 280 ▪ Medical or surgical procedures. The medical condition that leads to the
281 procedure is the AE.
- 282 ▪ Hospital admissions where an untoward medical occurrence did not occur.
- 283 ▪ Day to day fluctuations of pre-existing disease or conditions present or detected
284 at the start of the study that do not worsen.
- 285 ▪ The condition/indication being studied or expected progression, signs, or
286 symptoms of the condition/indication being studied unless more severe than
287 expected for the subject's condition.
- 288 ▪ Post-operative findings of swelling or pain within two (2) weeks of the initial
289 procedure, unless deemed by the physician as of greater severity than expected.

290
291 *Follow-Up of Adverse Events*

292 After the initial AE report, the investigator is required to proactively follow each subject
293 until the event resolves. All AEs documented at a previous visit that are designated as
294 ongoing will be reviewed at subsequent visits/contacts.

295
296 Adverse events will be followed until resolution, until no further changes in the event are
297 expected (i.e. the point at which a subject experiencing a critical adverse event is treated
298 successfully and stabilized even though he/she may continue to experience lingering
299 sequelae that may never resolve), until the subject is lost to follow-up, or until it is agreed
300 that further follow-up of the event is not warranted (e.g. non-serious, study therapy

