372 2 groups and five outcome measures, and assuming an effect size of 0.20 (small) based on between group
373 differences we constructed a sample size estimation using a Multivariate Analysis of Variance
374 (MANOVA). Measuring global effects, with an expected 80% power, and a standard error of probability
375 of 0.05, we estimate the need for a minimum sample size of 70 for statistical significance (~35 per group).
376 To account for a 20% drop-out rate, a sample size of 84 subjects will be recruited. We will employ
377 intention to treat and a chains equation, multiple imputation method in which we will assign predictor,
378 structural and impute variables. Further, we will not oversample characteristics within each group for
379 drop-outs.
380
381

382 **11.2 Data Analyses**

383
384 Descriptive statistics will be used to describe both groups at baseline. Appropriate tests of differences will
385 be used to compare baseline differences in descriptive statistics, pain, range of motion, etc., between the
386 two groups (e.g., t-tests and chi-square). Adverse events, including severity of these events will be
387 captured and compared between the two groups. A Multivariate Analysis of Variance (MANOVA) will
388 be used to measure differences between the targeted outcome measure at each of the given timepoints
389 (baseline, 6-week, 3-month, 6-month, and 12-months post-injection time periods). A MANOVA
390 investigates the effects of a categorical predictive variable (groups) on 2 or more continuous outcomes,
391 which are correlated and represented by a vector of dependent variables. For all analyses, a p value of
392 <0.05 will be considered statistically significant.
393
394
395
396
397

398 **12. Bibliography**

- 399 1. Divine J, Zazulak B, Hewett TE. Viscosupplementation for knee osteoarthritis. Clin Orthop Rel
400 Res. 2006; 455:113-122.
- 401 2. Dawson J, Linsell L, Zondervan K, et al. Epidemiology of hop and knee pain and its impact on
402 overall health status in older adults. Rheumatology. 2004; 43:497-504.
403

404 3. Laupattarakasem W, Laopaiboon M, Laupattarakasem P, Sumananont C. Arthroscopic
405 debridement for knee osteoarthritis (Review). Cochrane Collaboration. Issue 4, 2009.
406 4. Younes M, et al. Systemic effects of epidural and intra-articular glucocorticoid injections in
407 diabetic and non-diabetic patients. *Joint Bone Spine*. 2007, 74(5): 472-6.

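### Section 7 treats significant-but-expected worsening of the study knee inconsistently, so a knee replacement attributed to expected progression may go unrecorded as an AE or SAE, and it is not a defined outcome

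*Combined protocol and SAP*

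**What the plan says.** Four sets of provisions in Section 7 bear on this point.

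- **Examples of an AE.** One is "Significant or unexpected worsening or exacerbation of the condition/indication" under study. Another is "Exacerbation of a chronic or intermittent pre-existing condition including either" a rise in its frequency or its intensity. Neither makes an exception for the study knee.
- **What an AE is not.** The list removes "The condition/indication being studied or expected progression, signs, or" "symptoms of the condition/indication being studied unless more severe than" expected for that subject. It also removes procedures as such: "Medical or surgical procedures. The medical condition that leads to the" procedure is what gets coded. A further entry removes "Hospital admissions where an untoward medical occurrence did not occur".
- **SAE definition.** An SAE is an adverse event that meets at least one listed criterion. The criteria include "requires in-subject hospitalization or prolongation of existing hospitalization" and surgery performed to avert permanent impairment.
- **Documentation.** AEs go on the CRF once the study procedure has taken place, and a diagnosis is preferred to separate signs and symptoms.

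Section 11.2 says that AEs and their severity will be "captured and compared between the two groups". Section 3.1 admits Kellgren-Lawrence grades 3 and 4. Arthroplasty of the study knee appears once, as an entry exclusion in Section 3.2.

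**The concern.** In grade 3-4 knee osteoarthritis followed for 12 months, surgery on the injected knee is among the most consequential events a subject can have, whether it is read as harm or as treatment failure. Whether it reaches the safety record turns on an investigator's view of what was expected for that subject, and Section 7 gives no standard for that view. Two investigators could classify the same course differently, one as an SAE and one as no event. The AE comparison in Section 11.2 and the SAE reporting in Section 8 both depend on that classification.

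The efficacy data are affected as well. The five primary questionnaires are collected up to 12 months. After a replacement they describe an operated knee, and nothing in the plan marks them as such.

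**Working it through.** No arithmetic settles this, and the plan states no figure to reproduce. The check sets the passages side by side.

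**Step 1: where the two lists agree and where they conflict.**

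| Course of the study knee | AE examples | Exclusion list | Result |
|---|---|---|---|
| Worsening that is unexpected or more severe than expected | AE | Exclusion lifted | AE under both |
| Worsening that is significant but expected | AE, because the example joins significant and unexpected with *or* | Not an AE | Conflict |
| Rise in frequency or intensity of the chronic condition, within expectation | AE | Not an AE | Conflict |
| Stable disease with day-to-day fluctuation | Not listed | Not an AE | Not an AE under both |

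The severity qualifier in the exclusion list settles the first row. It does not settle the second or third.

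**Step 2: follow a study-knee replacement that the investigator attributes to expected progression.**

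1. The operation is not itself an AE; Section 7 redirects to the condition behind it.
2. That condition is osteoarthritis progression within expectation, which the exclusion list removes.
3. The admission can also be removed, if no untoward occurrence is judged to lie behind it.
4. The hospitalization and surgical-intervention criteria apply only to something that is already an AE. With no AE there is no SAE.

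If the investigator relies on the AE examples instead, step 2 gives an AE, and hospitalization makes it an SAE. The text supports both paths.

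**Step 3: look for another provision that requires the event to be recorded.**

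- Endpoints (Section 2): the questionnaires and inflammatory markers only.
- Prohibited treatments (Section 5): oral steroids, steroid injections and viscosupplementation for the first 6 months. Surgery is not mentioned.
- Withdrawal reasons (Section 3.3): surgery is not named. An SAE is, but that presupposes the classification in doubt.
- AE assessment at each visit (Schedule of Events): it applies the same Section 7 definitions.
- 12-month radiograph (Section 5): it would show an implant in a subject who attends, but no endpoint or analysis uses it.
- Operative notes (Section 9): named as source documents, with no CRF item or analysis tied to them.
- Statistical procedures (Section 11): nothing on study-knee surgery or on scores collected after it.

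**Step 4: consequence for the primary scores.** If the event is classed as an SAE, the investigator may withdraw the subject, and any scores then missing fall to the multiple imputation in Section 11.1. If it is not classed as an AE and the subject stays, post-surgical scores are analysed with no marker. The same clinical course can therefore produce different data, depending on the reading of Section 7.

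**The case against.** The strongest reply is that Section 7 is largely sound. It codes the diagnosis rather than the procedure, and it counts both surgical intervention and hospitalization toward seriousness. A subject who worsens markedly and is admitted for arthroplasty fits two of the AE examples, and worse-than-expected worsening is an AE under both lists. All of this stands, and it limits the gap to worsening judged expected.

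A reader might infer more than the documents support in four ways.

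- *That surgery is never counted.* It is counted whenever the underlying condition is an AE.
- *That a replacement would go unseen.* AE assessment at every visit, the 12-month radiograph, operative notes and documented withdrawal reasons could each reveal it. What is missing is a requirement to record it as a study event.
- *That one arm is favoured.* Section 3 blinds subjects and investigators for the whole study, so the judgement of what is expected is made without knowledge of the arm. Inconsistent classification may add noise; no direction is shown.
- *That a number of lost events can be stated.* If 3% to 10% of the 84 subjects were operated on, that would be 84 × 0.03 = 2.5 to 84 × 0.10 = 8.4 operations. These rates are assumptions, and the counts are ceilings, because only operations judged expected could be lost. Similarly, 3 operated subjects of 42 in one arm, each scoring an assumed 30 points higher, would move that arm's mean by 3 × 30 / 42 = 2.1 points. Equal numbers and gains in both arms would cancel, and a score taken soon after an operation could be lower instead.

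It is also fair to say that keeping post-surgical scores is compatible with intention to treat. The defect is that they cannot be identified, not that they are kept.

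**Conclusion.** The point holds in a limited form. Section 7 gives two answers for significant-but-expected worsening of the study knee and leaves expected undefined. Because procedures are captured only through their underlying condition, and every SAE must first be an AE, a study-knee replacement attributed to expected progression may be recorded as neither. It is not a defined outcome, and scores from operated subjects who remain in the study enter the primary comparison unmarked.

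The size cannot be given from the documents: they state neither a surgery rate nor the share of operations that would be judged expected. The conclusion rests on the wording alone and on the premise that some progression in a grade 3-4 population can reasonably be called expected. It does not put the design in doubt, but it leaves a hole in the Section 11.2 safety comparison that is cheap to close.

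**What to change.** 1. Reconcile the Section 7 passages on worsening of the study condition, so that significant-but-expected worsening has one classification, and say how expected is to be judged.
2. Add one CRF item, asked at the existing visits: any surgery on, or hospitalization for, the study knee since randomization, with date and reason. Complete it whether or not the event is judged expected progression, and assess each event against the existing SAE criteria.
3. In Section 11.2, tabulate these events by arm.
4. Flag questionnaires completed after such surgery and report a sensitivity analysis that takes the flag into account, keeping the intention-to-treat analysis as primary.

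The cost is protocol wording, one extra CRF item and a few more SAE reports, some of which will be judged unrelated. No visit is added, and the change concerns recording and analysis only.
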